### **3.5 Unblinding**

The pharmacy Dresden will provide a closed envelope for each medication number containing the information whether a patient is in the Sorafenib or in the Placebo group. The closed envelopes will be deposited at the Dresden pharmacy and at the local center treating the patients. In case of an adverse event that makes it necessary for the treating physician to obtain this information, the envelope can be opened (unblinding). In case of unblinding the Safety Desk should be informed immediately via fax.

After the end of the trial, the envelopes have to be given back to the Studienzentrale via the visiting monitor. The event of obtaining the information on the nature of the investigational drug has to be documented in the file and in the CRF.

## **4 STUDY, STANDARD AND CONCOMITANT TREATMENTS**

### **4.1 Investigational product and Placebo**

Sorafenib (BAY-43-9006) is an oral cytostatic Raf kinase inhibitor, PDGFR inhibitor, VEGFR-2 (KDR) inhibitor, Flt3 and c-Kit inhibitor. For more details of the preclinical and clinical information please refer to chapter 1.3.1 and to the current Nexavar® Prescribing Information (Fachinformation).

#### **4.1.1 Relevant physical, chemical and pharmaceutical properties**

The drug product for supply of clinical trials is a 200 mg coated tablet (calculated as free base Sorafenib). The formulation is presented as an immediate release dosage form, i.e. the active ingredient is completely dissolved under in-vitro test conditions within a short period of time. The tablet cores contain Sorafenib tosylate and the excipients croscarmellose sodium, microcrystalline cellulose, hydroxypropylmethyl cellulose, sodium lauryl sulfate and magnesium stearate. The film-coat consists of hydroxypropylmethyl cellulose, polyethylene glycole, titanium dioxide and red iron oxide. The tablets have a red color in appearance, a weight of 350 mg, and a 10 mm round shape. For blinding purpose in clinical trials, corresponding Placebo tablets are available.

#### **4.1.2 Instructions for storage and handling**

The stability profile of the drug substance is good. The current retest period for storage at room temperature is 30 months. In addition, the drug substance is insensitive to the influence of light. The tablets are packaged in HDPE bottles. They should only be stored in the pack provided. The storage temperature should not exceed 25°C.

#### **4.1.3 Interactions with concomitant medications**

Sorafenib has the ability to inhibit a variety of liver metabolic enzymes in vitro. The clinical impact of this inhibition in humans taking drugs metabolized by these enzymes is unknown. Therefore, all patients enrolled onto this trial who are taking concomitant medications that are known to be metabolized by the liver should be closely observed for side effects of these concomitant medications. Furthermore, patients taking narrow therapeutic index medications, including the following should be monitored proactively:

- Warfarin
- Quinidine
- Digoxin

#### 4.1.4 Effect of food

When given with a high-fat meal, Sorafenib absorption was reduced. Therefore, Sorafenib/ Placebo should be administered fasting or with a moderate-fat meal.

#### 4.1.5 Dose modification and delays of Sorafenib or Placebo

The modifications of Sorafenib or Placebo will follow the following pre-defined dose levels:

Dose level 1 (starting dose):	400 mg BID (2 tablets twice a day)
Dose level 2:	400 mg QD (2 tablets once a day)
Dose level 3:	400 mg QOD (2 tablets every second day)

Table 2: Sorafenib dose levels

Please note that the dose of 400 mg BID (total daily dose 800 mg) is the standard dose. If a dose reduction below 400 mg QOD (2 tablets every other day) is required, the patient should be discontinued from the study treatment. After resolution of the adverse event, the dose may be re-escalated from dose level 2 or 3 to the starting dose (see table) at the discretion of the investigator. As a general rule, grade 3 toxicity should be followed by permanent dose reduction. Exceptions are skin toxicities as defined below.

Resolution of an adverse event is defined as disappearance or reduction of the adverse event to below grade 3 toxicity. For patients with toxicities  $\geq$  grade 2 present at baseline (before start of Sorafenib/ Placebo treatment), resolution to maximum grade 1 level will apply.

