##### 4.1.5.1 Dose modification for hematological toxicity

Hematological toxicities will be considered not relevant for dose modification during the period of chemotherapy and the expected subsequent myelosuppression. However, these criteria will apply after hematopoietic recovery from the last chemotherapy course during the subsequent maintenance therapy.

Toxicity	Grade 1	Grade 2	Grade 3*	Grade 4*
Hematologic	Continue at the same dose level.	Continue at the same dose level.	Withhold dose until toxicity is grade <2, then resume treatment at the same dose level. If patient experiences a second grade 3 toxicity, withhold dose until toxicity is grade <2, then reduce dose to 400 mg p.o. QD and resume treatment.	Withhold dose until toxicity is grade <2, then reduce dose to 400 mg p.o. QD and resume treatment, or discontinue at the discretion of the principal investigator after discussion with study sponsor (safety desk at SAL).

\*Patients who develop grade 3 leukopenia, or grade 3/ grade 4 lymphopenia may continue Sorafenib/ Placebo treatment without interruption at the discretion of the investigator.

Table 3: Dose modifications and delays for hematologic toxicities of Sorafenib/ Placebo

Table 4 summarizes the recommendations for dose delays and modifications for all non-hematologic adverse events, except for skin toxicities and hypertension, which will be detailed separately (Table 5, Table 6, Table 7). These recommendations pertain, if the adverse event is considered to be related to Sorafenib/ Placebo, but not to the chemotherapy.

Toxicity	Grade 1	Grade 2	Grade 3*	Grade 4*
Non-hematologic	Continue at the same dose level.	Continue at the same dose level.	Withhold dose until toxicity is grade <1, then resume treatment at the same dose level. If patient experiences a second grade 3 toxicity, withhold dose until toxicity is grade <1, then reduce dose to 400 mg p.o. QD and resume treatment.	Withhold dose until toxicity is grade <1, then reduce dose to 400 mg p.o. QD. and resume treatment, or discontinue at the discretion of the principal investigator after discussion with study sponsor.

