#### 4.1.5.3 Dose modifications for hypertension

An increased incidence of hypertension was observed in Sorafenib-treated patients. Hypertension was usually mild to moderate, occurred early in the course of treatment, and was amenable to management with standard antihypertensive therapy. Blood pressure should be monitored regularly and treated, if required, in accordance with standard medical practice. In cases of severe or persistent hypertension, or hypertensive crisis despite adequate antihypertensive therapy, permanent discontinuation of Sorafenib/ Placebo should be considered. In general, hypertension should be treated according to Table 7.

Management of treatment-emergent hypertension	
Grade of Event (CTCAE v3)	Management / next dose
Grade 1: asymptomatic and transient	Consider increased BP monitoring
Grade 2: asymptomatic and diastolic BP < 110 mmHg	Begin anti-hypertensive therapy and continue Sorafenib/ Placebo
Grade 2: symptomatic / persistent OR Diastolic BP ≥ 110 mmHg OR Grade 3	Sorafenib/ Placebo should be stopped* until symptoms resolve and diastolic BP returns to ≤ 100 mmHg. Treat subject with anti-hypertensives. When Sorafenib/ Placebo is re-started, reduce to 400 mg p.o. QD and possibly re-escalate dose later at the discretion of treating physician. If diastolic BP is not controlled to ≤ 100 mmHg on therapy, reduce Sorafenib/ Placebo to 400 mg p.o. every other day (QOD) and monitor BP closely If BP is not controlled on Sorafenib/ Placebo 400 mg p.o. QOD, study treatment should be discontinued
Grade 4: life-threatening	Discontinue Sorafenib/ Placebo permanently (end of study)
Please note the distinction between asymptomatic and symptomatic grade 2 hypertension. * Subjects requiring a delay of > 28 days should go off protocol therapy (end of study).	

*Table 7: Suggested dose modifications for Sorafenib/ Placebo-associated hypertension*

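### Section 4.1.5 sets permanent dose reduction as the general rule after grade 3 toxicity with only skin exempted, but Tables 3 and 4 resume the same dose after a first grade 3 event

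*Protocol*

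**What the plan says.** **General rule.** Section 4.1.5 of the protocol says "As a general rule, grade 3 toxicity should be followed by permanent dose reduction" and continues "Exceptions are skin toxicities as defined below". No other class is exempted. The sentence just before the rule says that after resolution "the dose may be re-escalated from dose level 2 or 3 to the starting dose (see table) at the discretion of the investigator", with no limit by grade. The section then defines resolution as the event having disappeared or fallen below grade 3. A stricter limit applies to patients who already had toxicity of grade 2 or more at baseline.

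**Table 3 (hematologic).** First grade 3 event: "Withhold dose until toxicity is grade <2, then resume treatment at the same dose level". Second event: "If patient experiences a second grade 3 toxicity, withhold dose until toxicity is grade <2, then reduce dose to 400 mg p.o. QD and resume". Section 4.1.5.1 applies these criteria in maintenance, after hematopoietic recovery. Section 4.3.3.1 also refers to Table 3 when blood counts have not regenerated by day 35 of consolidation.

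**Table 4 (non-hematologic, except skin toxicity and hypertension).** First grade 3 event: "Withhold dose until toxicity is grade <1, then resume treatment at the same dose level". Again the dose falls to 400 mg once daily only after a second event. The table covers events attributed to Sorafenib/Placebo and not to chemotherapy.

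**Footnotes to Tables 3 and 4.** Patients with certain listed grade 3 events "may continue Sorafenib/ Placebo treatment without interruption at the discretion of the investigator".

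**Table 7 (hypertension).** The row that includes grade 3 says to stop and, on restart, "reduce to 400 mg p.o. QD and possibly re-escalate dose later at the discretion of treating physician".

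**The concern.** A site with a patient who has a first grade 3 event outside the skin class finds two instructions in the same section. The text points to a lasting reduction; the table for that toxicity class points to a return to the same dose. Nothing says which prevails.

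Three things are at stake. The first is patient safety and delivered dose, because the dose after a first severe event bears on the risk of a repeat. The second is the toxicity comparison, a secondary objective in section 2.3.2, which becomes harder to interpret if the dosing rule behind it is unclear. The third is the per-protocol analysis in section 7.2, which keeps only patients treated in full adherence to the protocol. A patient restarted at the same dose after a first grade 3 event follows Table 3 or 4 and departs from the general rule; a patient reduced for good does the opposite.

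**Working it through.** The protocol states no figure to reproduce here. The check compares the instructions and adds dose arithmetic from Table 2.

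**Step 1. Consequence of a first grade 3 event, by source**

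| Source | Class | After a first grade 3 event | Called permanent? |
|---|---|---|---|
| Section 4.1.5, text | All except skin | Dose reduction | Yes |
| Table 3 | Hematologic | Withhold, then same dose level | No reduction |
| Table 4 | Other non-hematologic, drug-related | Withhold, then same dose level | No reduction |
| Footnotes to Tables 3 and 4 | Listed events | May continue uninterrupted | No reduction |
| Table 7 | Hypertension | Stop, restart reduced, possibly re-escalate | No |
| Table 6 | Skin (exempt) | Interrupt, restart reduced for 28 days, then full dose if controlled | No |

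**Step 2. Can the tables simply override the text?** Tables 3, 4, 6 and 7 together cover hematologic, other non-hematologic, skin and hypertension events. None imposes permanent reduction after a first grade 3 event. If the tables prevail, the general rule governs no first event. The exemption for skin would then have no purpose, and the exempt class would be handled more strictly after a first event (reduced restart in Table 6) than the classes under the rule (same dose in Tables 3 and 4).

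**Step 3. Size for one patient on the starting dose** (dose levels from Table 2)
- Tables 3 and 4: 400 mg twice daily = 2 × 400 = 800 mg/day.
- General rule, one level dropped: 400 mg once daily = 400 mg/day. Ratio 800 / 400 = 2.
- General rule, two levels dropped: 400 mg every other day = 400 / 2 = 200 mg/day on average. Ratio 800 / 200 = 4.

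The general rule does not say how many levels to drop. One level is an assumption, and the range of the ratio is 2 to 4.

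**Step 4. Secondary tensions**
- *Re-escalation.* The text allows return to the starting dose without a limit by grade, next to a rule that calls the grade 3 reduction permanent. Table 7 allows possible re-escalation in a row that includes grade 3, although hypertension is not a named exception.
- *Restart criterion.* Resolution means below grade 3 in the text, but Table 3 requires grade <2 and Table 4 grade <1 before treatment resumes.

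**The case against.** The best defence is that the sentence is hedged (a general rule, worded as what should happen), that Table 4 is introduced as recommendations and Table 7 as suggestions, and that a physician treating a specific event will use the table for its class. The hedge is real, so a reader who infers that the protocol orders permanent reduction after any non-skin grade 3 event goes beyond the text. It does not remove the conflict, because the section lists its exceptions and names only skin.

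The secondary tensions are open to a milder reading. Re-escalation can serve reductions made for other grades, such as grade 2 skin events or grade 4 events, and the next sentence may be meant to limit it for grade 3. The Table 7 row mixes symptomatic or persistent grade 2, diastolic pressure of at least 110 mmHg and grade 3. The definition of resolution follows the re-escalation sentence and may not have been meant as a restart threshold. These points need clarifying but are weaker than the conflict with Tables 3 and 4.

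A reader might also infer a large effect on the trial. The documents do not support that:
- Different dosing between sites is what the text permits; nothing shows that it occurs.
- Grade 3 rates of 31% (renal) and 39% (liver) on Sorafenib in section 6.3.1.5 do not count the patients affected. They come from single-agent trials in other cancers, the placebo rates were 22% and 24% (differences of 9 and 15 percentage points), and they include hand-foot reaction (6% and 8%), which is exempt, and diarrhea (2% and 10%), which the Table 4 footnote sets apart.
- Over a full year of maintenance the gap would be 365 × 800 mg = 292 g against 365 × 400 mg = 146 g. That is one patient's extreme: an event on the first day, no time withheld, no second event and the whole year completed.
- Both arms follow the same blinded rules and the primary analysis is by intention to treat, so the ambiguity is not a source of bias in the EFS comparison. At most it makes delivered dose more variable.

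**Conclusion.** The contradiction stands. For a first grade 3 event that falls under Table 3 or Table 4 and not under their footnotes, section 4.1.5 gives two different consequences, and neither precedence nor the listed exceptions resolves them. For a patient on the starting dose the two differ by a factor of 2 in daily dose if the general rule means one level down. Adherence after such an event cannot be decided for the per-protocol analysis.

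The point is limited to Table 3's scope (maintenance, plus the day-35 reference in consolidation) and Table 4's scope (events judged drug-related). It changes neither the intention-to-treat comparison nor the sample size, power or alpha. The number of patients affected cannot be estimated from the document. No view is taken on which rule is clinically right.

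**What to change.** The sponsor should reconcile the text of section 4.1.5 with Tables 3, 4 and 7 and the footnotes to Tables 3 and 4, so that each toxicity class has:
- one stated consequence of a first grade 3 event and one of a repeat event, including how many dose levels change and whether the change is permanent;
- one statement on whether re-escalation is allowed;
- one criterion for restarting treatment.

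The section should also say whether the text or the table prevails if they differ, and the per-protocol adherence criterion should refer to the reconciled rule. The clinical team decides which rule applies.

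The cost is wording in section 4.1.5 and its tables, with no added patients, visits or procedures.

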##### 4.1.5.1 Dose modification for hematological toxicity

Hematological toxicities will be considered not relevant for dose modification during the period of chemotherapy and the expected subsequent myelosuppression. However, these criteria will apply after hematopoietic recovery from the last chemotherapy course during the subsequent maintenance therapy.

Toxicity	Grade 1	Grade 2	Grade 3*	Grade 4*
Hematologic	Continue at the same dose level.	Continue at the same dose level.	Withhold dose until toxicity is grade <2, then resume treatment at the same dose level. If patient experiences a second grade 3 toxicity, withhold dose until toxicity is grade <2, then reduce dose to 400 mg p.o. QD and resume treatment.	Withhold dose until toxicity is grade <2, then reduce dose to 400 mg p.o. QD and resume treatment, or discontinue at the discretion of the principal investigator after discussion with study sponsor (safety desk at SAL).

\*Patients who develop grade 3 leukopenia, or grade 3/ grade 4 lymphopenia may continue Sorafenib/ Placebo treatment without interruption at the discretion of the investigator.

Table 3: Dose modifications and delays for hematologic toxicities of Sorafenib/ Placebo

Table 4 summarizes the recommendations for dose delays and modifications for all non-hematologic adverse events, except for skin toxicities and hypertension, which will be detailed separately (Table 5, Table 6, Table 7). These recommendations pertain, if the adverse event is considered to be related to Sorafenib/ Placebo, but not to the chemotherapy.

Toxicity	Grade 1	Grade 2	Grade 3*	Grade 4*
Non-hematologic	Continue at the same dose level.	Continue at the same dose level.	Withhold dose until toxicity is grade <1, then resume treatment at the same dose level. If patient experiences a second grade 3 toxicity, withhold dose until toxicity is grade <1, then reduce dose to 400 mg p.o. QD and resume treatment.	Withhold dose until toxicity is grade <1, then reduce dose to 400 mg p.o. QD. and resume treatment, or discontinue at the discretion of the principal investigator after discussion with study sponsor.
*Patients who develop grade 3 fever/ chills, grade 3 elevation of hepatic transaminases with ALT and AST <10x ULN, grade 3 hyperlipasemia or hyperamylasemia without clinical or other evidence of pancreatitis may continue Sorafenib/ Placebo treatment without interruption at the discretion of the investigator. Also excludes nausea/ vomiting that has not been premedicated, and diarrhea. If no recovery after 30 day delay, treatment will be discontinued unless patient is deriving clinical benefit. If more than 2 dose reductions are required, treatment will be discontinued.				

*Table 4: Dose modifications for Sorafenib-associated non hematological toxicity except hand-foot skin reactions and hypertension*

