#### 4.1.5.2 Dose modifications for skin toxicity

Only for the purpose of dose delays and modifications, patients experiencing Hand-Foot syndrome should have their signs and symptoms graded according to the following system (see Table 5). Other skin toxicities will be graded according to CTCAE Version 3.0. Please note that Hand Foot Syndrome will be graded and recorded as an adverse event according to CTCAE Version 3.0 in the CRF. These recommendations pertain, if the adverse event is considered to be related to Sorafenib/ Placebo, but not to the chemotherapy.

Grade 1	Numbness, dysesthesia/ paresthesia, tingling, painless swelling or erythema of the hands and/ or feet and/ or discomfort, which does not disrupt normal activities
Grade 2	Painful erythema and swelling of the hands and/ or feet and/or discomfort affecting the patient's activities
Grade 3	Moist desquamation, ulceration, blistering or severe pain of the hands and/or feet and/or severe discomfort that causes the patient to be unable to work or perform activities of daily living.

*Table 5: Grading for Hand-Foot Syndrome*

According to the grade and incidence of skin toxicity (including rash and hand-foot syndrome) for a given patient, the following dose modification schedule will be followed.

Skin toxicity grade	Occurrence	Suggested Dose modification
Grade 1: Numbness, dysethesia, paresthesia, tingling, painless swelling, erythema or discomfort of the hands or feet which does not disrupt the patients normal activity	Any occurrence	Institute supportive measures immediately and continue Sorafenib/Placebo treatment
Grade 2: Painful erythema and swelling of the hands or feet and/or discomfort affecting the patient's normal activities	1 st occurrence	Institute supportive measures and consider a decrease of Sorafenib/Placebo dose to 400mg daily for 28 days If toxicity resolves or returns to grade 0–1 after dose reduction, increase Sorafenib/Placebo to full dose after 28 days If toxicity does not resolve or return to grade 0-1 despite dose reduction, interrupt Sorafenib/Placebo treatment for a minimum of 7 days, until toxicity has resolved or returned to grade 0–1. When resuming treatment after dose interruption, re-start Sorafenib/Placebo at reduced dose of 400mg daily for 28 days If toxicity remains absent or at grade 0–1 at reduced dose, increase Sorafenib/ Placebo to full dose after 28 days

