	2 nd or 3 rd occurrence	Decrease dose to 400mg daily for the study period, do not re-escalate the dose
	4 th occurrence	Decision whether to discontinue Sorafenib/ Placebo treatment should be made based on clinical judgment and patient preference
Grade 3: Moist desquamation, ulceration, blistering or severe pain of the hands or feet, or severe discomfort that causes inability to work or perform activities of daily living	1 st occurrence	Institute supportive measures and interrupt Sorafenib/ Placebo treatment for a minimum of 7 days and until toxicity has resolved or is reduced to grade 0–1 When resuming treatment after dose interruption, re-start Sorafenib/Placebo at reduced dose of 400mg daily for 28 days If toxicity remains absent or at grade 0–1 at reduced dose, increase Sorafenib/ Placebo to full dose after 28 days
	2 nd occurrence	Decrease dose to 400 mg daily for the study period, do not re-escalate the dose
	3 rd occurrence	Decision whether to discontinue Sorafenib/ Placebo treatment should be made based on clinical judgment and patient preference

Table 6: Suggested Dose Modifications for Sorafenib/ Placebo for Hand-Foot Skin Reaction

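### Tables 3 and 4 give a fixed 400 mg QD as the reduced dose, which is no reduction for a patient already at dose level 2

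*Protocol*

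**What the plan says.** Section 4.1.5 ties all modifications to the levels of Table 2: level 1 is 400 mg BID, level 2 is 400 mg QD and level 3 is 400 mg QOD. It also sets the floor: "If a dose reduction below 400 mg QOD (2 tablets every other day) is required, the patient should be discontinued from the study treatment".

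Section 4.1.5.1 then gives the action cells.

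- Table 3 (hematologic), grade 3: "If patient experiences a second grade 3 toxicity, withhold dose until toxicity is grade <2, then reduce dose to 400 mg p.o. QD".
- Table 4 (non-hematologic), grade 3: "If patient experiences a second grade 3 toxicity, withhold dose until toxicity is grade <1, then reduce dose to 400 mg p.o. QD".
- Table 4, grade 4: "Withhold dose until toxicity is grade <1, then reduce dose to 400 mg p.o. QD. and resume treatment, or discontinue". The Table 3 grade 4 cell has the same structure. In both tables the choice to discontinue follows discussion with the sponsor.

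Neither table mentions QOD. The Table 4 footnote nevertheless allows for two steps: "If more than 2 dose reductions are required, treatment will be discontinued". Section 4.3.3.1 (Arm V) sends the reader to Table 3 when counts have not recovered by day 35, and excludes the patient only when more than two levels of reduction would be needed.

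**The concern.** A cell that names an absolute dose is correct from only one starting level. The cells were evidently written for a patient on the starting dose, but the protocol's other rules move patients to 400 mg QD for other reasons, in some cases for the rest of the study.

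For such a patient, a site that follows the cell restarts the dose on which the toxicity occurred. A site that follows Table 2 halves it. The stake is dosing safety after serious toxicity and consistency between sites, in a trial that lists the comparison of toxicity among its secondary objectives (2.3.2).

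**Working it through.** The protocol states no figure to reproduce. The check compares the dose named in the cells with each starting level, then asks whether the protocol itself creates the problem case.

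**1. Daily dose per level** (Table 2; 200 mg tablets per 4.1.1)

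- Level 1: 2 tablets × 2 per day × 200 mg = 800 mg/day
- Level 2: 2 tablets × 1 per day × 200 mg = 400 mg/day
- Level 3: 2 tablets × 200 mg every second day = 400 / 2 = 200 mg/day on average

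**2. Effect of the printed dose, 400 mg QD**

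- From level 1: (400 − 800) / 800 = −50%, the intended single step.
- From level 2: (400 − 400) / 400 = 0%. One level down would be (200 − 400) / 400 = −50%.
- From level 3: 400 mg QD lies above the current dose, so the cell cannot be carried out as a reduction. Section 4.1.5 implies discontinuation there, but the cell does not say so.

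**3. Number of steps available**

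- Table 2: three levels, hence 3 − 1 = 2 reductions before stopping.
- Table 4 footnote and 4.3.3.1: up to 2.
- Table 7 (hypertension): QD, then QOD, then stop, hence 2.
- Tables 3 and 4 as printed: 1.

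The clearest mismatch is in 4.3.3.1: it allows up to two levels of reduction and points to Table 3 for carrying them out, but Table 3 prints only one.

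**4. Ways a patient can already be at level 2**

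- Table 6, second or third grade 2 occurrence: "Decrease dose to 400mg daily for the study period, do not re-escalate the dose". The second grade 3 occurrence carries the same restriction. These two rows hold the patient at level 2.
- Table 7: restart at QD after hypertension. Re-escalation is possible but discretionary.
- An earlier grade 4 event under Table 3 or 4, resumed at QD and not re-escalated.
- A reduction under the other table, for example a hematologic reduction followed by non-hematologic toxicity.
- Temporarily, after a first grade 2 skin reaction: "consider a decrease of Sorafenib/Placebo dose to 400mg daily for 28 days". Full dose returns if the reaction settles, so this window is short.

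One route drops out. A patient who is at level 2 because of a second grade 3 event under the same table would next have a third, and the cell covers only the second. There the table is silent rather than wrong.

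**5. What must then happen.** A first grade 3 event under a table resumes at the same dose. The conflict therefore needs a second grade 3 event under that table while at level 2, or a grade 4 event after which the site resumes instead of discontinuing.

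**The case against.** The best defence is that 4.1.5 governs. It ties every modification to the Table 2 levels, and the cells say to reduce. Since restarting QD at level 2 reduces nothing, a careful reader returns to Table 2 and finds QOD. The grade 4 cells also offer discontinuation after contact with the sponsor, which limits variation between sites. Table 4 is introduced as recommendations, and section 3.4 requires withdrawal for unacceptable toxicity or an interruption of more than 28 days.

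Much of this stands, and it limits the weight of the point. It does not remove it. The inference to QOD overrides the dose printed in the cell, and sections 3.4 and 4.1.5 do not say which dose to resume at level 2.

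Two stronger readings are tempting and should not be adopted:

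- A reader might infer that the cells double the dose at level 3, from an average of 200 to 400 mg/day. That requires reading a reduction instruction as an increase, against the stopping rule in 4.1.5. The supportable statement is that the cell cannot be applied there.
- A reader might infer a breach of the rule in 4.1.5, "As a general rule, grade 3 toxicity should be followed by permanent dose reduction". This is weak support. It is stated only as a general rule, re-escalation is discretionary, and the same grade 3 cells already resume the same dose after a first event. The firmer evidence is Table 2, the Table 4 footnote, 4.3.3.1 and Table 7.

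**Conclusion.** The point holds as a defect in the dosing instructions. In four cells the printed dose is right from level 1 and wrong from level 2, where it gives a 0% change instead of the 50% reduction to the next level. It rests on the cells being followed as printed, and on the patient having reached and stayed at level 2 by one of the routes above.

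A reader might go on to infer that many patients would be affected, because skin reactions and hypertension are common with sorafenib. The protocol does not support any such number: its incidence tables come from single-agent use in other cancers, and the problem case needs further severe toxicity at level 2. Nor is there any effect on power, type I error or the ITT primary analysis. The correction should be made because it removes an unsafe ambiguity at very little cost.

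**What to change.** In the second-grade-3 and grade 4 cells of Tables 3 and 4, replace the fixed 400 mg QD instruction with: *reduce by one dose level (Table 2); discontinue if already at dose level 3*. In the two grade 3 cells, extend the trigger to *second or later* grade 3 toxicity, so that a third event is covered. Keep the grade 4 option to discontinue.

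This leaves the action from level 1 unchanged, supplies the second step that the Table 4 footnote and 4.3.3.1 presuppose, and matches the sequence in Table 7. The cost is an amendment to the wording of four cells, with no extra visits, patients or analyses.
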